Assessment of immature platelets was introduced as a non-invasive test of real time thrombopoiesis. They are newly released in the circulation with a larger size & greater RNA content than mature platelets, and can be measured by automated hematology analyzer equipped with reticulocyte detection channel and described as immature platelet fraction (IPF-%) and absolute immature platelet count (A-IPC). A high IPF-% has been suggested as an indicator of thrombocytopenia due to rapid platelet consumption, while a low IPF-% is characteristic of bone marrow suppression states. IPF-%/A-IPC has the competency to be performed routinely and, therefore, can provide therapeutic and diagnostic feedback in the compatible life threatening conditions (**Hong et al., 2013**).

Aim of work

The aim of this work is to show the utility of estimating IPF-% and A-IPC using a reticulocyte detection channel CBC auto analyzer as a simple reproducible blood analysis to be employed in the differential diagnosis of pregnancy-associated thrombotic microangiopathic conditions.

Patients and Methods

This study aiming to show the utility of estimating IPF-% and A-IPC using a reticulocyte detection channel CBC auto analyzer as a simple reproducible blood analysis to be employed in the differential diagnosis of pregnancy-associated thrombotic microangiopathic conditions. Patients were recruited from Ain Shams University Maternity Hospital.

Study sample was 57 women and were classified into three groups:

Group 1: *SPE/HELLP group.* This group will include 24 pregnant women (gestational age of >20 weeks) who are diagnosed as having TMA with provisional diagnosis of pre-eclampsia, HELLP syndrome.

Group 2: *TTP/HUS group.* This group will include 13 pregnant women (gestational age of >20 weeks) who are diagnosed as having TMA with provisional diagnosis of TTP/HUS.

Group 3: *Control group.* This group will include 20 pregnant women (gestational age of >20 weeks) having normal pregnancy with normal blood pressure and platelet count.

Inclusion criteria

Women will be included if they are:

- Older than 20 years of age
- Pregnant with singleton intrauterine pregnancy
- More than 20 weeks of gestation

Exclusion criteria

Patients will be excluded from the study if there was any of the following:

- Congenital malformation and fetuses with chromosomal or genetic syndrome.

- Recent blood transfusion.
- Refusal to participate in the study.
- BMI <18.

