4) Total platelet count: There was high significant difference between the three groups regarding total platelet count ($p < 0.001$). Applying Conover test reveal; significant difference between SPE/HELLP and control, between TTP/HUS and control and between SPE/HELLP and TTP/HUS (**Table 16**), (**Figure 19**).

5) Immature platelet count A-IPC : There was significant difference between the three groups regarding immature platelet count ($p < 0.05$). Applying Conover test reveal; significant difference between SPE/HELLP and control, between TTP/HUS and control (**Table 16**), (**Figure 20**).

6) Immature platelet fraction IPF-%: There was high significant difference between the three groups regarding immature platelet fraction ($p < 0.001$). Applying Conover test reveal; significant difference between SPE/HELLP and control, between TTP/HUS and control and between SPE/HELLP and TTP/HUS (**Table 16**), (**Figure 21**).

Table (16): Total platelet count, immature platelet count, and immature platelet fraction in patients with SPE/HELLP or TTP/HUS and normal controls

Assessment of Immature Platelet Fraction in Pregnancy-Associated Thrombotic Microangiopathy: (Results)

Variable	SPE/HELLP (n=24)	TTP/HUS (n=13)	Control (n=20)	χ^2	DF	P-value
Total platelet count (*1,000/mm³)	121 (73 – 188.5) [†]	53.0 (37.0 – 81.0) ^{†‡}	269.5 (235.0 – 337.0)	35.333	2	<0.0001
Absolute Immature platelet count (*1,000/mm³) (A-IPC)	14.875 (11.781 – 22.151) [†]	11.64 (6.410 – 21.238) [†]	21.992 (16.945 – 25.431)	10.362	2	0.006
Immature platelet fraction (%) (IPF-%)	13.0 (9.6 – 22.9) [†]	19.5 (15.1 – 27.7) ^{†‡}	7.2 (6.2 – 11.1)	18.897	2	<0.0001

Data are median (interquartile range).

[†]P-value <0.05 versus Control group (Conover test).

[‡]P-value <0.05 versus SPE/HELLP group (Conover test).

[figure not shown]

Figure (19): Box plot showing the total platelet count in patients with SPE/HELLP or TTP/HUS and normal controls.

Assessment of Immature Platelet Fraction in Pregnancy-Associated Thrombotic Microangiopathy: (Results)

[figure not shown]

Figure (20): Box plot showing the immature platelet count (IPC) in patients with SPE/HELLP or TTP/HUS and normal controls.

[figure not shown]

Figure (21): Box plot showing the immature platelet fraction (IPF) in patients with SPE/HELLP or TTP/HUS and normal controls.

Assessment of Immature Platelet Fraction in Pregnancy-Associated Thrombotic Microangiopathy: (Results)

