- **Prevalence of a low platelet count (A-IPC):** There was high significant difference between the three groups regarding prevalence of a low platelet count ($P < 0.001$) (Table 17), (Figure 22).
- **Prevalence of high IPF-%:** There was significant difference between the three groups regarding prevalence of high IPF ($P < 0.05$) (Table 17), (Figure 22).
- **Prevalence of high schistocyte count:** There was high significant difference between the three groups regarding prevalence of high schistocyte count ($P < 0.001$) (Table 17), (Figure 22).

Table (17): Prevalence of a low platelet count, high IPF, or high schistocyte count among patients with SPE/HELLP or TTP/HUS and normal controls

Variable	SPE/HELLP (n=24)	TTP/HUS (n=13)	Control (n=20)	P-value¶
Low total platelet count ($< 100,000/\text{mm}^3$)	9 (37.5%)	11 (84.6%)	0 (0.0%)	< 0.001
High IPF-% ($> 11.2\%$) (Machin, 2010)	14 (58.3%)	10 (76.9%)	5 (25.0%)	0.008
High schistocyte count ($> 1\%$) (Gina et al., 2011)	14 (58.3%)	11 (84.6%)	0.01 (0.0%)	< 0.001

Data are number (%).

¶Fisher's exact test.

Assessment of Immature Platelet Fraction in Pregnancy-Associated Thrombotic Microangiopathy: (Results)

[figure not shown]

Figure (22): Prevalence of a low platelet count, high IPF, or high schistocyte count among the studied groups.

✚ Receiver-operating characteristic (ROC) curve analysis

Table (18): Receiver-operating characteristic (ROC) curve analysis for discrimination between patients with TTP/HUS or SPE/HELLP using the IPF or schistocytes count

Index	Marker
-------	--------

Assessment of Immature Platelet Fraction in Pregnancy-Associated Thrombotic Microangiopathy: (Results)

	IPF	Schistocyte count
Positive group (TTP/HUS)	13 (35.1%)	13 (35.1%)
Negative group (SPE/HELLP)	24 (64.9%)	24 (64.9%)
Area under the ROC curve (AUC)	0.692 (0.519 to 0.833)	0.771 (0.603 to 0.893)
z statistic	2.028	3.022
P-value	0.043¶	0.003¶
Associated cut-off criterion	>15.9 %	>4.6 %
Sensitivity (%)	76.92 (46.2 - 95.0)	61.54 (31.6 - 86.1)
Specificity (%)	66.67 (44.7 - 84.4)	91.67 (73.0 - 99.0)
Positive predictive value (PPV, %)	55.6 (30.8 - 78.5)	80.0 (44.4 - 97.5)
Negative predictive value (NPV, %)	84.2 (60.4 - 96.6)	81.5 (61.9 - 93.7)

Diagnostic indices are presented as value (95% CI).

¶DeLong method.

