Figure (25): Comparison of ROC curves for discrimination between patients with TTP/HUS or SPE/HELLP using the IPF or schistocyte count.

Assessment of Immature Platelet Fraction in Pregnancy-Associated Thrombotic Microangiopathy: (Results)

Table (20): ROC curve analysis for discrimination between patients with TMA and normal controls using the IPF-%s or schistocyte count

Index	IPF-%	Schistocyte count
Positive group (TMA)	37 (64.9%)	37 (64.9%)
Negative group (normal controls)	20 (35.1%)	20 (35.1%)
Area under the ROC curve (AUC)	0.820 (0.695 to 0.909)	0.838 (0.716 to 0.922)
z statistic	5.678	8.660
P-value	<0.0001¶	<0.0001¶
Associated cut-off criterion	>8.1 %	>0 %
Sensitivity (%)	86.49 (71.2 - 95.5)	67.57 (50.2 - 82.0)
Specificity (%)	65.00 (40.8 - 84.6)	100.00 (83.2 - 100.0)
Positive predictive value (PPV, %)	82.1 (66.5 - 92.5)	100.0 (86.3 - 100.0)
Negative predictive value (NPV, %)	72.2 (46.5 - 90.3)	62.5 (43.7 - 78.9)

Diagnostic indices are presented as value (95% CI).

¶DeLong method.

- **(ROC) curve analysis for discrimination between patients with TMA or control using the IPF-%:** The optimal cutoff values for IPF-% for discrimination between patients with TMA or control was >8.1%. The sensitivity and specificity were 86.49% and 65%, respectively. The positive predictive value (PPV) and negative predictive value (NPV) were 82.1 % and 72.2%, respectively (**Table 20**), (**Figure 26**).

Assessment of Immature Platelet Fraction in Pregnancy-Associated Thrombotic Microangiopathy: (Results)

[figure not shown]

Figure (26): ROC curve for discrimination between patients with TMA and normal controls using the IPF.

- **(ROC) curve analysis for discrimination between patients with TMA or control using schistocyte count:** The optimal cutoff values for schistocyte count for discrimination between patients with TMA and normal controls was >0 %. The sensitivity and specificity were 67.57 % and 100%, respectively. The PPV and NPV were 100 % and 62.5%, respectively (**Table 20**), (**Figure 27**).

Assessment of Immature Platelet Fraction in Pregnancy-Associated Thrombotic Microangiopathy: (Results)

[figure not shown]

Figure (27): ROC curve for discrimination between patients with TMA and normal controls using the schistocyte count.

- **Comparison of the receiver-operating characteristic (ROC) curves:**

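### The printed AUC intervals treat the AUC as a proportion of all women and ignore the group split; for IPF-% in TTP/HUS versus SPE/HELLP a better-calibrated interval includes 0.5, so that result is borderline

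*SAP*

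**What the plan says.** SAP Table 18 (repeated from Table 7) reports the IPF-% AUC for TTP/HUS (n=13) versus SPE/HELLP (n=24) as "0.692 (0.519 to 0.833", with z = 2.028 and P = 0.043. In Table 20 (repeated from Table 9) the schistocyte AUC for TMA (n=37) versus controls (n=20) is "0.838 (0.716 to 0.922", with z = 8.660. Tables 8, 10, 19, 21 and 25 carry the same intervals forward. Table 24 adds the combined model at 0.827 (0.667 to 0.931).

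In Tables 7, 9, 18 and 20 the footnote "DeLong method" is attached to the P-values. The only note on the intervals is "Diagnostic indices are presented as value (95% CI", which names no method. The Statistical methods section of the protocol mentions no ROC analysis, no interval method and no significance level. The aim in the protocol is a simple blood test "to be employed in the differential diagnosis of pregnancy-associated thrombotic microangiopathic conditions". No primary analysis is named, so the weight given here to the contrast between the two patient groups is inferred from that aim.

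**The concern.** A DeLong P-value with an interval beside it reads as one analysis. The printed interval, however, cannot be obtained from the printed z. If it comes from a formula that does not fit an AUC, its stated 95% level is unreliable, and by an amount that depends on group sizes, spread and ties.

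At stake is the contrast closest to the study's aim. The printed lower limit of 0.519 and P = 0.043 both place the IPF-% AUC just on the favourable side of 0.5. With 13 and 24 women, the choice of method can decide which side it falls on.

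**Working it through.** **Inputs.** AUC, z and group sizes from SAP Tables 18, 20 and 24.

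**1. Reproduce the printed P.** 2 × (1 − Φ(2.028)) = 0.0426, printed as 0.043. The implied standard error is (0.692 − 0.5)/2.028 = 0.0947. The plain DeLong interval is then 0.692 ± 1.96 × 0.0947 = 0.506 to 0.878, which is not the printed one.

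**2. Reproduce the printed intervals.** Exact binomial (Clopper-Pearson) limits with x = AUC × n successes in n women:

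| AUC | n | Binomial limits | Printed |
|---|---|---|---|
| IPF-%, TTP/HUS vs SPE/HELLP, 0.692 | 37 | 0.519–0.833 | 0.519–0.833 |
| Schistocytes, same groups, 0.771 | 37 | 0.604–0.893 | 0.603–0.893 |
| Combined model, 0.827 | 37 | 0.667–0.931 | 0.667–0.931 |
| IPF-%, TMA vs control, 0.820 | 57 | 0.696–0.909 | 0.695–0.909 |
| Schistocytes, TMA vs control, 0.838 | 57 | 0.717–0.922 | 0.716–0.922 |

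All five agree within 0.001. For IPF-%, x = 0.692 × 37 = 25.6 women, but the AUC is an average over 13 × 24 = 312 pairs.

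**3. Logit-DeLong intervals from the printed z.** SE = (AUC − 0.5)/z, and the limits are logit(AUC) ± 1.96 × SE/[AUC(1 − AUC)], transformed back. For IPF-%: logit(0.692) = 0.8095; 0.0947/(0.692 × 0.308) = 0.444; 0.8095 ± 0.8706 = −0.061 to 1.680; back-transformed, **0.485 to 0.843**.

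| AUC | SE | Logit-DeLong |
|---|---|---|
| IPF-%, TTP/HUS vs SPE/HELLP | 0.0947 | 0.485–0.843 |
| Schistocytes, same groups | 0.0897 | 0.554–0.901 |
| Combined model | 0.0746 | 0.632–0.930 |
| IPF-%, TMA vs control | 0.0564 | 0.683–0.906 |
| Schistocytes, TMA vs control | 0.0390 | 0.746–0.901 |

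**4. Coverage at 13 versus 24** (60,000 simulated data sets per row, normal data):

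| True AUC; SD of the 13 relative to the 24 | Binomial | Plain DeLong | Logit-DeLong |
|---|---|---|---|
| 0.5; equal | 91.8% | 93.6% | 96.0% |
| 0.692; equal | 92.1% | 92.8% | 95.8% |
| 0.5; half | 93.7% | 93.9% | 96.1% |
| 0.5; double | 87.4% | 93.0% | 96.1% |

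In the three rows with true AUC 0.5, the DeLong z-test rejects in 6.4%, 6.1% and 7.0% of data sets, so P = 0.043 is also slightly optimistic.

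**5. Why the error goes the other way for schistocytes against controls.** At a cut-off above 0%, Table 20 gives sensitivity 67.57% (25 of 37) and specificity 100% (20 of 20). All controls are therefore tied at zero with 12 TMA patients, and the AUC is (25 + 0.5 × 12)/37 = 0.838. In the DeLong calculation all its variability comes from the 37 patients: SE = 0.5 × √[(25/37)(12/37)/36] = 0.039, the value implied by the printed z. The binomial formula cannot see these ties and gives a wider interval.

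**6. Exact rank test for IPF-%.** U = 216 is the only value that gives an AUC of 0.692 (216/312 = 0.6923). Without ties, the exact two-sided P is 0.0576.

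**The case against.** The strongest reply is that nothing has been miscalculated. P follows from z, the interval is a correctly computed binomial interval, and the DeLong symbol does not claim to cover it. That stands: this is a choice of method, not an arithmetic slip. It does not rescue the interval, because the formula chosen does not describe an AUC.

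A second reply is that the exact rank test is no clear improvement on DeLong. This also stands in part. It tests equality of the two distributions, not AUC = 0.5. In the simulations its continuity-corrected normal form rejected in 4.5% of data sets with equal spread, but in 3.3% or 7.7% when the smaller group had half or double the spread. It therefore belongs beside the DeLong P as a sensitivity result, and the logit-DeLong interval is the firmer evidence.

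A third reply is that the consequence is small. The SAP text on this ROC curve draws no significance claim from P = 0.043. Its claims of significance for IPF-% between the two patient groups rest on the Conover test (P < 0.05) and on the combined logistic model (P = 0.031, Table 23); the model adjusted for gestational age gives 0.043 (Table 11). Nothing here shows any of those to be wrong.

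A reader might infer that IPF-% has been shown not to separate TTP/HUS from SPE/HELLP. The documents do not support that: the estimate is unchanged, the plain DeLong interval still excludes 0.5, and the analyses just named still favour IPF-%. Nor may one infer that every printed interval flatters the marker, as step 5 shows.

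**Conclusion.** The concern holds as a fault of method. All five distinct AUC intervals in the SAP come from a formula that ignores the group split and ties, and they do not match the DeLong tests. For IPF-% in TTP/HUS versus SPE/HELLP, the printed interval has simulated coverage of about 87–94%, depending on the spread in each group. An interval with coverage of about 96% includes 0.5. The evidence from this AUC is borderline, neither established nor refuted.

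No other AUC conclusion against 0.5 changes: the remaining logit-DeLong lower limits are 0.554, 0.632, 0.683 and 0.746.

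Assumptions: standard errors are recovered from the printed AUC and z; the simulations use normal data; and the exact P assumes no ties in IPF-%. About 14 of the 37 values would have to share one tie to bring the rank-test P below 0.05, which is implausible for this measure. The 0.05 threshold is taken from the SAP's usage, since no level is stated.

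**What to change.** - Recalculate the AUC intervals in Tables 7–10, 18–21, 24 and 25 as logit-transformed DeLong intervals from the individual data, for the single markers and the combined model. The values in step 3 show what to expect.
- State the interval method in the table footnotes.
- Describe the IPF-% AUC for TTP/HUS versus SPE/HELLP as borderline. Beside the DeLong P of 0.043, give the exact rank-sum P of 0.058 (U = 216 of 312, recomputed if there are ties) as a sensitivity result, and note that it tests equal distributions.
- Keep the Conover and logistic results as they are.

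The cost is recalculation and a few words of text; no new data are needed. The downside for the sponsor is that the IPF-% interval in this contrast will no longer exclude 0.5.

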Figure (6): Box plot showing the immature platelet count (IPC) in patients with SPE/HELLP or TTP/HUS and normal controls. Box represents the range from the first to third quartile (interquartile range). Line inside the box represents the median (second quartile). Whiskers represent the range between the minimum and maximum values excluding outliers (rounded markers).

Assessment of Immature Platelet Fraction in Pregnancy-Associated Thrombotic Microangiopathy: (Results)

[figure not shown]

Figure (7): Box plot showing the immature platelet fraction (IPF) in patients with SPE/HELLP or TTP/HUS and normal controls. Box represents the range from the first to third quartile (interquartile range). Line inside the box represents the median (second quartile). Whiskers represent the range between the minimum and maximum values.

Assessment of Immature Platelet Fraction in Pregnancy-Associated Thrombotic Microangiopathy: (Results)

Table (6): Prevalence of a low platelet count, high IPF, or high schistocyte count among patients with SPE/HELLP or TTP/HUS and normal controls

Variable	SPE/HELLP (n=24)	TTP/HUS (n=13)	Control (n=20)	P-value¶
Low total platelet count (<100,000/mm ³)	9 (37.5%)	11 (84.6%)	0 (0.0%)	<0.001
High IPF (>11.2%) (Machin, 2010)	14 (58.3%)	10 (76.9%)	5 (25.0%)	0.008
High schistocyte count (>0%) (Gina et al.,2011)	14 (58.3%)	11 (84.6%)	0 (0.0%)	<0.001

Data are number (%).

¶Fisher's exact test.

[figure not shown]

Figure (8): Prevalence of a low platelet count, high IPF, or high schistocyte count among patients with SPE/HELLP or TTP/HUS and normal controls.

Table (7): Receiver-operating characteristic (ROC) curve analysis for discrimination between patients with TTP/HUS or SPE/HELLP using the IPF or schistocyte count

Marker

Assessment of Immature Platelet Fraction in Pregnancy-Associated Thrombotic Microangiopathy: (Results)

Index	IPF	Schistocyte count
Sample size	37	37
Positive group (TTP/HUS)	13 (35.1%)	13 (35.1%)
Negative group (SPE/HELLP)	24 (64.9%)	24 (64.9%)
Area under the ROC curve (AUC)	0.692 (0.519 to 0.833)	0.771 (0.603 to 0.893)
z statistic	2.028	3.022
P-value	0.043¶	0.003¶
Associated cut-off criterion	>15.9 %	>4.6 %
Sensitivity (%)	76.92 (46.2 - 95.0)	61.54 (31.6 - 86.1)
Specificity (%)	66.67 (44.7 – 84.4)	91.67 (73.0 – 99.0)
Positive predictive value (PPV, %)	55.6 (30.8 - 78.5)	80.0 (44.4 - 97.5)
Negative predictive value NPV, %)	84.2 (60.4 - 96.6)	81.5 (61.9 - 93.7)

Diagnostic indices are presented as value (95% CI).

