- **(ROC) curve analysis for discrimination between patients with TTP/HUS or SPE/HELLP using the IPF-%:** The optimal cutoff values for IPF-% for discrimination between patients with TTP/HUS or SPE/HELLP was >15.9 %. The sensitivity and specificity were 76.92% and 66.7%, respectively. The positive predictive value (PPV) and negative predictive value (NPV) were 55.6 % and 84.2%, respectively (AUC=0.692) (**Table 18**) (**Figure 23**).

Assessment of Immature Platelet Fraction in Pregnancy-Associated Thrombotic Microangiopathy: (Results)

[figure not shown]

Figure (23): Receiver-operating characteristic (ROC) curve analysis for discrimination between patients with TTP/HUS or SPE/HELLP using the IPF.

Assessment of Immature Platelet Fraction in Pregnancy-Associated Thrombotic Microangiopathy: (Results)

- **(ROC) curve analysis for discrimination between patients with TTP/HUS or SPE/HELLP using the schistocyte count:** The optimal cutoff values for schistocyte count for discrimination between patients with TTP/HUS or SPE/HELLP was $>4.6\%$. The sensitivity and specificity were 61.54% and 91.67% , respectively. The positive predictive value (PPV) and negative predictive value (NPV) were 80% and 81.5% , respectively (AUC=0.771) (Table 19), (Figure 24).

[figure not shown]

Figure (24): Receiver-operating characteristic (ROC) curve analysis for discrimination between patients with TTP/HUS or SPE/HELLP using the schistocyte count.

Comparison of the receiver-operating characteristic (ROC) curves:

Comparison of the receiver-operating characteristic (ROC) curves between IPF-% or schistocyte count revealed no significant difference between IPF-% and schistocyte count regarding discrimination between patients with TTP/HUS or SPE/HELLP (P-value >0.05) (Table 19), (Figure 25).

Assessment of Immature Platelet Fraction in Pregnancy-Associated Thrombotic Microangiopathy: (Results)

Table (19): Comparison of ROC curves for discrimination between patients with TTP/HUS or SPE/HELLP using the IPF or schistocyte count

Index	IPF	Schistocyte count	Difference	z	P-value¶
Area under ROC (AUC)	0.692 (0.519 to 0.833)	0.771 (0.603 to 0.893)	0.079 (-0.171 to 0.328)	0.617	0.537

Diagnostic indices are presented as value (95% CI).

¶DeLong method.

Assessment of Immature Platelet Fraction in Pregnancy-Associated Thrombotic Microangiopathy: (Results)

[figure not shown]

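### Three of the four ROC cut-offs called optimal, and the combined model, appear to be chosen and scored in the same women with no internal validation, so the printed sensitivities and specificities are optimistic on average

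*SAP*

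**What the plan says.** The SAP is a results chapter. Its ROC text attaches the label optimal to four cut-offs:

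- TTP/HUS against SPE/HELLP, IPF: "The optimal cutoff values for IPF-% for discrimination between patients with TTP/HUS or SPE/HELLP was >15.9" per cent (text after Table 18).
- TTP/HUS against SPE/HELLP, schistocytes: "The optimal cutoff values for schistocyte count for discrimination between patients with TTP/HUS or SPE/HELLP was" above 4.6% (same section).
- TMA against controls, IPF: "The optimal cutoff values for IPF-% for discrimination between patients with TMA or control was >8.1" per cent (text after Table 20).
- TMA against controls, schistocytes: "The optimal cutoff values for schistocyte count for discrimination between patients with TMA and normal controls was >0" per cent (same section).

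The only limits credited to a source are in the prevalence tables. Table 6 has "High IPF (>11.2"%) and "High schistocyte count (>0"%). Table 17 repeats the IPF limit but prints the schistocyte limit as >1%.

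Tables 18 and 20 give sensitivity, specificity, PPV and NPV with 95% intervals, for example "76.92 (46.2 - 95.0") for the sensitivity of IPF in Table 18. Tables 23 and 24 fit a logistic model with both markers to the 37 patients and report 92.3% sensitivity and 62.5% specificity. The available text gives no probability cut-off for that pair (Figure 30 is not shown).

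The protocol's Statistical methods section ends at Spearman correlation. It contains no ROC analysis, cut-off rule, logistic model or validation step.

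**The concern.** A cut-off picked because it performs best in a sample also picks up that sample's chance pattern. Scored in the same women, it will on average look better than it would in new ones. With 13 TTP/HUS cases, moving one woman across the threshold changes sensitivity by 1/13, or 7.7 points, so there is much room for tuning.

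The protocol's aim is to show that IPF-% and A-IPC are useful in differential diagnosis, and a reader will carry away the accuracy at the proposed cut-offs. The consent information says that results do not alter the care of the women studied. The exposure is therefore in later use of the cut-offs.

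**Working it through.** **Step 1. Reproduce the printed figures.** Counts follow from the percentages and group sizes. The exact (Clopper-Pearson) limits are the 0.025 quantile of Beta(x, n−x+1) and the 0.975 quantile of Beta(x+1, n−x).

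| Rule | Sensitivity | Specificity |
|---|---|---|
| IPF >15.9% (Table 18) | 10/13 = 76.9% (46.2–95.0) | 16/24 = 66.7% (44.7–84.4) |
| Schistocytes >4.6% (Table 18) | 8/13 = 61.5% (31.6–86.1) | 22/24 = 91.7% (73.0–99.0) |
| IPF >8.1% (Table 20) | 32/37 = 86.5% (71.2–95.5) | 13/20 = 65.0% (40.8–84.6) |
| Combined (Table 24) | 12/13 = 92.3% (64.0–99.8) | 15/24 = 62.5% (40.6–81.2) |

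All 20 printed intervals for sensitivity, specificity, PPV and NPV in Tables 18, 20 and 24 reproduce in this way. They make no allowance for choosing the cut-off.

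**Step 2. Were the cut-offs cited beforehand?** The values 15.9, 4.6 and 8.1 equal none of the cited limits (11.2 for IPF; 0 or 1 for schistocytes). The >0% rule in Table 20 equals the Table 6 limit, so it is left out. Table 17's >1% carries the same counts as Table 6, and 14 of 24 SPE/HELLP women above 1% cannot go with a group median of 0.5%. The two labels need reconciling.

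**Step 3. How much rests on the choice?** Youden index J = sensitivity + specificity − 1.

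- IPF >15.9%: 0.769 + 0.667 − 1 = 0.436. At the cited 11.2%: 10/13 + 10/24 − 1 = 0.186.
- Schistocytes >4.6%: 0.615 + 0.917 − 1 = 0.532. At >0%: 11/13 + 10/24 − 1 = 0.263.
- IPF >8.1%: 0.865 + 0.650 − 1 = 0.515. At 11.2%: 24/37 + 15/20 − 1 = 0.399.
- Combined model: 0.923 + 0.625 − 1 = 0.548.

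These gaps show sensitivity to the choice. They do not measure optimism, because a different cut-off can be truly better.

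**Step 4. Illustrative optimism.** This is the apparent J minus the true J at the re-selected cut-off, under a maximum-Youden rule (assumed) and three sets of assumed distributions.

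| Cut-off | Reconstructed data matching printed quartiles, counts and AUC, bootstrapped | Simulated populations with the same counts | Equal-variance binormal, AUC at the estimate and both CI limits |
|---|---|---|---|
| IPF >15.9% | 0.066–0.109 | 0.05–0.10 | 0.141–0.192 |
| Schistocytes >4.6% | 0.056–0.094 | 0.09–0.12 | 0.124–0.184 |
| IPF >8.1% | 0.080–0.101 | 0.08–0.11 | 0.098–0.134 |

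With a closest-to-corner rule instead, the binormal setting gives 0.079–0.141 over the three. In the reconstructed data, re-selecting the IPF cut-off in resamples of 13 and 24 moved it between about 10.2% and 25.5% (5th to 95th percentile).

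For the combined model with refitting, joint reconstructions give J optimism of 0.090–0.145 and two independent binormal markers give 0.182–0.230. AUC optimism is 0.007–0.038 and 0.026–0.051 respectively.

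**Step 5. Do the intervals fail?** In simulations with re-selection, the exact intervals covered the true sensitivity or specificity at the chosen cut-off in about 92% to 98% of runs.

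**Step 6. Bias against sampling error.** At IPF >15.9%, SE(J) = sqrt(0.769×0.231/13 + 0.667×0.333/24) = 0.151.

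**The case against.** The defence has real substance. The conclusions comparing markers rest on AUCs, and the group differences in Table 16 use no cut-off. None of these changes. For IPF >15.9% the reconstructed optimism is smaller than the sampling error of 0.151, and an interval of 46% to 95% already warns the reader. The SAP prints the group ratios, and its closing text admits that the combined AUC was not significantly better than either marker. All of that stands, and it limits the reach of the point.

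A reader might go further in four ways that the documents do not support:

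- **That the intervals are badly wrong.** They ignore the selection, but they are wide and conservative, and simulated coverage stays near nominal.
- **That the figures must be too high.** Optimism is an average. In simulation the apparent J fell below the true one in roughly one sample in ten (8% to 14%).
- **That the values in Step 4 yield corrected results.** They rest on an unstated rule and on shapes assumed between printed quartiles. For the combined model the two approaches do not even overlap.
- **That all four cut-offs are affected.** The >0% schistocyte rule equals the limit cited in Table 6.

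None of this explains why three values without a cited source are scored only in the women who appear to have supplied them.

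**Conclusion.** The point holds in limited form. IPF >15.9%, schistocytes >4.6% and IPF >8.1% appear to be chosen and evaluated in the same 37 or 57 women. The combined model's coefficients, and apparently its operating point, come from the same 37. With no internal validation described, sensitivity and specificity are optimistic on average.

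Under the assumed maximum-Youden rule the size is about 0.05 to 0.19 in sensitivity plus specificity for the single markers and 0.09 to 0.23 for the combined model, depending on assumed distributions. These are illustrations; the actual correction needs patient-level data. Single-marker AUCs are not affected, and the combined AUC only slightly (about 0.01 to 0.05). That the cut-offs came from the data is inferred from the label optimal, the absence of a cited source and the absence of any planned rule. The documents do not say so outright.

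**What to change.** 1. State the rule that defined optimal, and the probability cut-off behind 92.3% and 62.5% in Table 24.
2. Bootstrap the whole procedure within group, with at least 1000 resamples, re-selecting each cut-off by that rule and refitting the combined model. Print optimism-corrected sensitivity and specificity beside the apparent values in Tables 18, 20 and 24, and the corrected AUC in Table 24. Note that in samples this small the bootstrap may remove only part of the optimism.
3. Keep the exact intervals, labelled as conditional on the chosen cut-off. Do not replace them with bootstrap percentile limits shifted by the optimism: in simulation those covered only about 85% to 89% for sensitivity with 13 cases and for specificity with 20 controls.
4. Label the three cut-offs and the combined model as exploratory and not validated. Add one sentence saying that PPV and NPV apply only at the sample ratios of 13/37 and 37/57 (so the schistocyte NPV in Table 20, "62.5 (43.7 - 78.9"), is 20/32 at that mix) and that the combined AUC was not significantly better than either marker alone.

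The cost is a little analysis time and less favourable accuracy figures. No new patients or samples are needed.
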